9. RESEARCH DESIGN AND METHODS

All subjects would continue to receive standard and customary postoperative analgesics, so there is no risk of subjects receiving a lower degree of analgesia than if they otherwise did not enroll in the study. The cryoneurolysis procedure will be done in addition to our current UCSD standard practice.

Study Overview

Day 0 Subjects randomized and cryoneurolysis/sham procedure administered

Days 0-4, 7, 14, 21 Pain levels, opioid consumption, and other end points collected [inspiratory spirometry for hospitalized subjects following video-assisted thoracoscopic surgery will occur at various time points as part of standard care and will be collected via EPIC]

Months 1, 3, 6, 12 Brief pain inventory administered [range-of-motion measurements following knee and shoulder arthroscopy as well as rotator cuff repair will occur at various time points as part of standard care and will be collected via EPIC]

Year 3 Cancer recurrence investigated for subjects with cancer-related procedures

Subjects will be individuals undergoing unilateral or bilateral mastectomy; upper or lower limb amputation; primary, unilateral total knee or shoulder arthroplasty; primary, unilateral rotator cuff repair; video-assisted thoracoscopic surgery; and burn-related skin grafting of the lateral thigh. Those who consent to participate in this study will have standard preoperative peripheral nerve blocks administered and catheters inserted: paravertebral blocks or a fascial plane block (e.g., erector spinae plane block) for mastectomy, femoral/sciatic for lower limb amputation, brachial plexus (or terminal nerves) for upper limb amputation; femoral or adductor canal for total knee arthroplasty; interscalene for shoulder arthroplasty or rotator cuff repair; thoracic epidural for video-assisted thoracoscopic surgery (VATS); and lateral femoral cutaneous nerve for skin grafting of the lateral thigh.

Treatment group assignment (randomization). Subjects with successfully-administered peripheral nerve blocks (defined by sensory changes in the appropriate nerve distribution) will be allocated to one of two possible treatments:

1. *cryoneurolysis*
2. *sham cryoneurolysis (placebo control)*

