Randomization will be stratified by surgery type (e.g., mastectomy, upper limb amputation, and lower limb amputation). Computer-generated randomization lists will be used to create sealed, opaque randomization envelopes with the treatment group assignment enclosed in each envelope labeled with the randomization number.

The specific nerves targeted will depend on the surgical site: intercostal nerves (4 levels depending on the specific surgical approach) for mastectomy; femoral/sciatic for lower limb amputation, brachial plexus (or terminal nerves) for upper limb amputation; infrapatellar branch of the saphenous nerve for knee arthroplasty; suprascapular nerve for shoulder surgery; intercostal nerves for VATS procedures, and the lateral femoral cutaneous nerve for skin grafting of the lateral thigh. The cryoneurolysis sites will be cleansed with chlorhexidine gluconate and isopropyl alcohol. Using the optimal ultrasound transducer for the specific anatomic location and subject anatomy (linear vs curvilinear array), the target nerves will be identified in a transverse cross-sectional (short axis) view.

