Incidence; duration each episode									•	•	•	•
Average & worst wound pain									•	•	•	•
Incidence; duration each episode									•	•	•	•

Difficulty sleeping due to pain?	•	•	•	•	•	•	•				
Awakenings due to pain	•	•	•	•	•	•	•				
Nausea (0=none, 10=vomited)	•	•	•	•	•	•	•				

* In addition to the above, for knee and shoulder surgery joint range of motion will be measured at various time points between 1-12 months as part of standard postoperative care; and for VATS, FEV1 will be measured at various time points during hospitalization as part of standard postoperative care.

Statistical Analysis. The limb amputation, total knee and shoulder arthroplasty, rotator cuff repair, VATS, and skin grafting subjects will be included in pilot studies to help power future clinical trials, so we will enroll a convenience sample and not have a pre-determined primary endpoint or statistical plan. However, the end points of most interest will be average pain score on postoperative day 2 for shoulder arthroplasty and skin grafting subjects, range-of-motion at 6 weeks for the rotator cuff repairs, range-of-motion for knee arthroplasty, and FEV1 for the VATS procedures.

For the subjects having mastectomy, we will power this study for an acute pain end point which will provide conclusive results for that end point; but, the data will also be used to help power a subsequent large, multicenter clinical trial for a chronic pain-related end point (which will require far more subjects than we will enroll for the current study).

For the mastectomy subjects, sample size calculations are centered around the hypothesis that cryoneurolysis decreases the incidence and severity of post-mastectomy pain in the week following surgery. To this end, the primary outcome is the average NRS (as administered as part of the Brief Pain Inventory) queried on the afternoon of postoperative day 2. The difference in the distribution of NRS between groups will be assessed using the Mann-Whitney U test. We approximate power using the two-sample t-test. Assuming a standard deviation of 2.25 NRS points,² and minimum clinically meaningful difference of 2 NRS points, n=30 patients per group provide 86% power with two-sided $\alpha=5\%$.

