10. HUMAN SUBJECTS

A convenience sample of subjects undergoing limb amputation (n=60), mastectomy (n=60), knee arthroplasty (n=60), shoulder arthroplasty and rotator cuff repair (n=60), VATS (n=60), and skin grafting of the lateral thigh (n=60) will be enrolled, with an additional 20 permitted to replace drop-outs. This will total up to 380 subjects.

Inclusion criteria: Adult patients of at least 18 years of age, (1) scheduled for a primary, unilateral total knee or shoulder arthroplasty, primary unilateral rotator cuff repair, VATS procedure, skin grafting of the lateral thigh, unilateral or bilateral mastectomy, or limb amputation distal to the femoral/humeral head and including at least one metatarsal/metacarpal bone; (2) a single-injection or continuous peripheral nerve block or epidural infusion planned for perioperative analgesia; and, (3) accepting of a cryoneurolysis procedure.

Exclusion criteria: (1) chronic opioid use (daily use within the 2 weeks prior to surgery and duration of use > 4 weeks); (2) pregnancy; (3) incarceration; (4) inability to communicate with the investigators; (5) morbid obesity (body mass index > 40 kg/m²); and, (6) possessing any contraindication specific to cryoneurolysis such as a localized infection at the treatment site, cryoglobulinemia, cold urticaria and Reynaud's Syndrome.

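### The only powered cohort mixes unilateral and bilateral mastectomy, and neither the stated randomisation strata nor the primary test takes laterality into account

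*Combined protocol and SAP*

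**What the plan says.** Under Statistical Analysis in section 9, mastectomy is the one cohort meant to give a firm answer: "For the subjects having mastectomy, we will power this study for an acute pain end point which will provide conclusive results for that end point". For the other cohorts the plan says "so we will enroll a convenience sample and not have a pre-determined primary endpoint or statistical plan".

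The powered cohort is mixed by design. Section 9 states "Subjects will be individuals undergoing unilateral or bilateral mastectomy", and the inclusion criteria in section 10 repeat it: "unilateral or bilateral mastectomy, or limb amputation distal to the femoral/humeral head".

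On allocation, section 9 says: "Randomization will be stratified by surgery type (e.g., mastectomy, upper limb amputation, and lower limb amputation". Amputation is divided there by limb; mastectomy is not divided. The lists are computer-generated and no block size is given.

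The primary outcome is one average NRS score per subject on postoperative day 2, and the analysis is given as: "The difference in the distribution of NRS between groups will be assessed using the Mann-Whitney U test". Nothing in the document makes laterality a stratum, covariate or subgroup. The planned between-group comparisons of demographic variables adjust nothing.

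**The concern.** A bilateral mastectomy is a larger operation than a unilateral one, so laterality may well be prognostic for a single whole-subject pain score. It is part of the eligibility description and so is known before allocation. With 30 subjects per arm, chance alone can leave one arm with noticeably more bilateral cases. If laterality is prognostic, two things follow. A visible imbalance would make a marginal primary result harder to defend, and an adjustment added afterwards would be post hoc. The variation between the two types of operation would also stay in the noise of the primary test, although it could be removed at almost no cost.

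**Working it through.** **Inputs from the plan (section 9, Statistical Analysis).** 30 per group; target difference 2 NRS points; SD 2.25 for the t-test calculation and 2.5 in the simulation; two-sided 5%; stated power 86% (t-test) and 89.5% (simulated Mann-Whitney).

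**Inputs assumed, because the documents give none.** Bilateral share 20-50%; NRS gap between bilateral and unilateral cases 0, 1 or 2 points; exact 30/30 split.

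**Step 1: the plan's own power.** Noncentrality = 2 / (SD × √(2/30)), with 58 degrees of freedom.
- SD 2.25: 2 / (2.25 × 0.2582) = 3.44, power 92.3%.
- SD 2.5: 2 / (2.5 × 0.2582) = 3.10, power 86.1%.

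The stated 86% therefore matches SD 2.5 and not the 2.25 given beside it. The simulated Mann-Whitney power at SD 2.5 comes to about 83%, not 89.5%; at SD 2.25 it is about 90%. This is a separate discrepancy and the laterality point does not depend on it. SD 2.5 is used below.

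**Step 2: chance of imbalance.** With K bilateral cases among 60, the number X in one arm is hypergeometric (60, K, 30), and the arms differ by |2X − K|.

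| Bilateral share (K) | P(differ by ≥6) | P(differ by ≥8) |
|---|---|---|
| 20% (12) | 10.4% | 2.1% |
| 30% (18) | 15.8% | 4.7% |
| 40% (24) | 18.7% | 6.4% |
| 50% (30) | 19.6% | 7.0% |

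If the number of bilateral cases is left random (binomial), the chance of a gap of 6 or more is 12-15% for shares of 30-50%.

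**Step 3: shift in the group difference.** Shift = gap × imbalance / 30. For 6 cases: 0 × 6/30 = 0; 1 × 6/30 = 0.2; 2 × 6/30 = 0.4 NRS points. Against the 2-point target that is 0%, 10% and 20%.

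**Step 4: type I error.** Scores were simulated as rounded normals limited to 0-10 with within-type SD 2.5, 40,000 trials per setting. Over all randomisations the planned test rejects a true null in 4.8-4.9% of trials. Conditional on an 8-case imbalance and a 2-point gap, the rate is about 10-11% at a 30-40% share and 9-10% at 50%.

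**Step 5: power.** Same model, effect 2, 40% bilateral, 4,000 trials per cell (simulation standard error about √(0.8 × 0.2/4000) = 0.6 points).

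| Gap | As planned | Stratified allocation, same test | Stratified allocation, van Elteren |
|---|---|---|---|
| 0 | 82.1% | 81.7% | 82.0% |
| 1 | 80.3% | 81.2% | 82.1% |
| 2 | 76.1% | 77.3% | 81.4% |

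The 40,000-trial run puts the planned test at 83.0%, 81.1% and 76.4% for gaps of 0, 1 and 2. It puts stratified allocation with the unchanged test at 81.8% and 78.3% for gaps of 1 and 2. Read together, the full change costs essentially nothing at no gap, gains about 1 point at a 1-point gap (82.1 − 81.1) and about 5 at a 2-point gap (81.4 − 76.4). Most of the gain comes from the test. Stratifying the allocation alone and keeping the plain test makes that test conservative (type I error about 3.3% at a 2-point gap).

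**The case against.** The case for leaving the plan alone is substantial.

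- **The stratum list is open.** It is introduced as an example and omits knee, shoulder, rotator cuff, thoracoscopic and skin-graft surgery, all of which are enrolled. A laterality split is unstated rather than excluded. This stands, and it is why the point is that the plan does not provide for laterality, not that it rules it out.
- **Randomisation already covers chance imbalance.** This stands for the unconditional properties: no bias on average and type I error near 5%. The ordinary 95% sampling range of the mean difference at SD 2.25 is ±1.96 × 2.25 × √(2/30) = ±1.14 points, so a shift of 0.2 or 0.4 is modest beside it.
- **The prognostic gap is assumed.** This stands. A 2-point gap would equal the plan's own minimum clinically meaningful difference and is an upper case; at zero there is no harm.
- **Laterality is one factor among several.** The cohort also mixes paravertebral with fascial plane blocks, and single-injection with continuous blocks. Upper- and lower-limb amputation target different nerves, which may explain why only amputation is split. This is fair: giving laterality priority is a judgement, resting on its being fixed at enrolment and named in the eligibility criteria.

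A reader might also infer that bilateral cases have more nerves treated. The protocol gives "intercostal nerves (4 levels depending on the specific surgical approach) for mastectomy" and does not say whether that is per side, so a difference in treatment extent is an inference only.

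**Conclusion.** The point holds as a moderate one about chance imbalance and precision in the only powered comparison. Under an assumed 20-50% bilateral share, a between-arm difference of 6 or more bilateral cases has a 10-20% chance. It matters only if laterality affects day-2 pain. The resulting shift is then 0.2 to 0.4 points for assumed gaps of 1 to 2 points, and the recoverable power is about 1 to 5 percentage points at a 30-40% share, with 2.5 taken as the SD within each type of operation.

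Two stronger readings are tempting, and the documents support neither. The first is that the primary analysis is biased or invalid: it is not, since overall type I error stays near 5%. The second is that ignoring laterality raises the planning SD from 2.25 to between 2.30 and 2.46 and so undermines the sample size. The plan does not describe 2.25 as a within-laterality SD, so laterality variation may already be in it. Even at 2.46, t-test power for a 2-point difference with 30 per group is 87%, above the stated 86%.

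**What to change.** 1. In section 9, Treatment group assignment, state that mastectomy is stratified as unilateral and bilateral. Replace the list of examples with the full list of strata, and state that allocation is blocked within each. Without blocking, separate lists would not secure balance.
2. In section 9, Statistical Analysis, make the laterality-stratified Wilcoxon (van Elteren) test the primary test for the mastectomy cohort in place of the unstratified Mann-Whitney test. The two changes belong together.
3. State whether the four intercostal levels for mastectomy are per side or in total, so that treatment extent in bilateral cases can be described.

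The cost of the first two is one more envelope list, a line of analysis text and one more possibly incomplete block at the end of enrolment. No subjects or procedures are added. The change should be made before outcome data are unmasked; if allocation has already begun, the stratified test can still be specified on its own.

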6. SPECIFIC AIMS

The ultimate objective of the proposed line of research is to determine if cryoanalgesia is an effective adjunctive treatment for pain in the period immediately following various painful surgical procedures; and, if this analgesic modality decreases the risk of persistent postoperative pain, or "chronic" pain. *The objective of the proposed pilot study is to optimize the protocol and collect data to power subsequent, definitive clinical trials.*

Specific Aim 1: To determine if, compared with current and customary analgesia, the addition of cryoanalgesia decreases the incidence and severity of post-surgical pain.

Hypothesis 1a (primary): The severity of surgically-related pain will be significantly decreased on postoperative day 2 with the addition of cryoanalgesia as compared with patients receiving solely standard-of-care treatment.

Hypothesis 1b: The incidence of chronic pain will be significantly decreased one year following surgery with the addition of cryoanalgesia as compared with patients receiving solely standard-of-care treatment.

Hypothesis 1c: The severity of chronic pain will be significantly decreased one year following surgery with the addition of cryoanalgesia as compared with patients receiving solely standard-of-care treatment.

[figure not shown]
Specific Aim 2: To determine if, compared with current and customary analgesia, the addition of cryoanalgesia improves postoperative functioning.

Hypothesis 2a: Following primary unilateral knee and shoulder arthroplasty as well as rotator cuff repair, joint range of motion will be significantly increased within the year following surgery with the addition of cryoanalgesia as compared with patients receiving solely standard-of-care treatment.

Hypothesis 2b: Following video-assisted thoracoscopic surgery, inspiratory spirometry will be improved within the month following surgery with the addition of cryoanalgesia as compared with patients receiving solely standard-of-care treatment.

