Brief Pain Inventory: The Brief Pain Inventory (short form) is an instrument specifically designed to assess pain and its impact on physical and emotional functioning within the previous 24 hours.^{22,23} It has established reliability and validity, with minimal inter-rater discordance, and is recommended by

the Initiative on Methods, Measurement, and Pain Assessment in Clinical Trials (IMMPACT) consensus statement.²⁴ The Brief Pain Inventory is comprised of three domains: (1) *pain*, with four questions involving “worst”, “average”, “least”, and “current” pain levels using a 0-10 Numeric Rating Scale (NRS; 0 = no pain; 10 = worst pain imaginable); (2) percentage of *relief* provided by pain treatments with one question (reported score is the percentage divided by 10 and then subtracted from 10: 0 = complete relief, 10 = no relief); and, (3) *interference* with 7 questions involving physical and emotional functioning using a 0-10 Likert scale (0 = no interference; 10 = complete interference). The use of both single items (e.g., average pain) and the composite score (0 = optimal; 120 = worst possible) is supported by the IMMPACT recommendations for assessing pain in clinical trials.²⁵⁻²⁷

Opioid consumption

Sleep disturbances: due to surgical pain

Range of motion: measured with a standard goniometer

Forced expiratory volume in 1 second (FEV1): measured with a standard inspiratory spirometer

Cancer recurrence: for subjects who underwent the surgical procedure related to a primary cancer, subjects' records will be investigated for indications of cancer recurrence up to 3 years following catheter placement (including estrogen receptor status as + or -). Patients may be contacted by phone if records suggest that the patient has not returned to the original surgeon within the previous 12 months.

The questionnaire will differentiate among multiple dimensions of breast and limb pain:

Phantom pain: painful sensations referred to the lost body part (breast or limb).

Phantom breast/limb sensations: non-painful sensations referred to the lost body part.

Wound pain: painful sensations localized to the portion of the body still present.

Summary of post-enrollment assessments (color added for clarity)

Time Point:	Postoperative Days								Postoperative Months			
	0	1	2	3	4	7	14	21	1	3	6	12
Opioid consumption	•	•	•	•	•	•	•	•	•	•	•	•
Average & worst pain [NRS]	•	•	•	•	•	•	•	•				
Brief Pain Inventory									•	•	•	•
Average & worst phantom pain									•	•	•	•

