12. INFORMED CONSENT

When a prospective subject desires, they will be provided information on the study purpose and protocol, as well as have any questions answered. Candidates who meet inclusion and exclusion criteria and desire study enrollment will be scheduled for their initial treatment. Written informed consent will be attained prior to any measurements or procedures the morning of surgery. This will occur in private patient care rooms, so that subjects may feel comfortable asking questions.

We do not foresee any issues relevant to the mental capacity of the potential human subjects. Written, informed consent will be attained prior to any study procedures or measurements. Following a history and physical by the site director, subjects will have an intravenous line inserted, external monitors placed, oxygen delivered by face mask, and conscious sedation provided for perineural catheter insertion. Therefore, subjects will not be sedated until following the written, informed consent process is completed.

Subjects will be provided privacy and time for decision making both in the study description/explanation telephone call to an investigator or research coordinator, as described above; and also the morning of the initial treatment using a private patient care room to again review the study, informed consent form, and answer any remaining subject questions. As noted previously, subjects may speak with an investigator by telephone from initial contact through the morning of treatment.

Surrogate consent will not be accepted; therefore, if human subjects cannot provide consent on their own, they will not be offered study enrollment. Consent by an individual's Legally Authorized Representative is unacceptable for study enrollment. Of note, minors (age < 18 years) will not be offered enrollment. Therefore, assent will not be accepted during the informed consent process.

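### No pain score is scheduled before the block and surgery, so one-year non-phantom pain cannot be split into pre-existing and post-surgical pain, nor pain severity adjusted for baseline

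*Combined protocol and SAP*

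**What the plan says.** Hypothesis 1b (section 6) states: "The incidence of chronic pain will be significantly decreased one year following surgery". Hypothesis 1c states: "The severity of chronic pain will be significantly decreased one year following surgery". Neither defines chronic pain, requires that it began after surgery, or refers to a change from a preoperative value.

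The one assessment table, in section 9, is titled "Summary of post-enrollment assessments". Its columns fall under "Postoperative Days" (0 to 21) and postoperative months (1 to 12). Average and worst pain on the NRS start at day 0, and the Brief Pain Inventory at month 1. The Study Overview in the same section also begins at day 0: "Pain levels, opioid consumption, and other end points collected".

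Day 0 is the day of randomization and of the active or sham procedure. Randomization follows a working block: "Subjects with successfully-administered peripheral nerve blocks (defined by sensory changes in the appropriate nerve distribution) will be allocated to one of two possible treatments".

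Section 12 says: "Written informed consent will be attained prior to any measurements or procedures the morning of surgery". It does not name those measurements. The statistical paragraphs of section 9 name demographic variables as the characteristics to be compared between groups, and use unadjusted Mann-Whitney and Fisher tests. Section 10 excludes chronic opioid use but not pre-existing pain.

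**The concern.** Hypotheses 1b and 1c concern persistent pain that follows surgery. Patients who come for knee or shoulder arthroplasty, rotator cuff repair or amputation may already have pain at the operated site. If that pain is unchanged a year later, the planned data record it in the same way as pain that the operation caused.

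Two things are at stake. The first is interpretation: a one-year proportion with pain cannot be read as an incidence of post-surgical pain. The second is precision: severity analyses lose a covariate that may be useful. Both matter because the documents say that these data are meant to help power later trials. A preoperative score that was not taken cannot be recovered reliably afterwards.

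**Working it through.** **1. Is there a usable baseline anywhere?**

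- Section 9 table: all columns are postoperative.
- Section 9 overview: pain collection starts on day 0. A score taken after randomization comes after a successful block and is not an untreated baseline. If a pre-block score was intended on day 0, the text does not say so.
- Section 12: measurements on the morning of surgery are mentioned, with no pain score among them.
- Section 10: prior pain is not an exclusion.
- Section 9 definitions: phantom pain is tied to the lost breast or limb and cannot pre-date its loss. Wound pain is any pain in the part that remains, with no condition on onset. The Brief Pain Inventory covers the previous 24 hours, again without onset.

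The gap therefore concerns wound pain, Brief Pain Inventory pain and the undefined chronic pain.

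**2. The plan's own power figure.** The plan gives none for one year. Its only figure is 86% for the mastectomy day-2 NRS (30 per group, difference 2, SD 2.25, two-sided 5%). By the noncentral t distribution those inputs give 92.3%; SD 2.5, used in the plan's simulation, gives 86.1%. That mismatch is a separate matter. Here it supplies the plan's own standardized effect: 2/2.25 = 0.89 or 2/2.5 = 0.80.

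**3. Gain from adjusting for a baseline score.** With correlation r between baseline and outcome, the residual SD is SD × √(1 − r²). Power is for a two-sample t-test at 30 per arm, two-sided 5%. The documents give no r, and the 0.6 SD effect is also an assumption.

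| Effect | r = 0 | 0.2 | 0.3 | 0.5 | 0.6 |
|---|---|---|---|---|---|
| 0.6 SD (assumed) | 62.8% | 64.5% | 66.8% | 75.1% | 81.5% |
| 0.89 SD (plan, SD 2.25) | 92.3% | 93.3% | 94.4% | 97.4% | 98.8% |

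**4. Dilution of the one-year proportion.** Assume new pain in p = 50% v 25%, and a share q whose old pain persists whatever the arm. The proportion with any pain is q + (1 − q)p; the proportion with new pain only is (1 − q)p. Power is exact Fisher at 30 per arm.

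| q | Any pain | Difference | Power | New pain only | Power |
|---|---|---|---|---|---|
| 0 | 50% v 25% | 25 points | 41.3% | 50% v 25% | 41.3% |
| 10% | 55% v 32.5% | 22.5 | 32.5% | 45% v 22.5% | 35.2% |
| 30% | 65% v 47.5% | 17.5 | 19.8% | 35% v 17.5% | 24.5% |

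Counting only new pain recovers 35.2 − 32.5 = 2.7 points at q = 10% and 24.5 − 19.8 = 4.7 points at q = 30%. The rest of the loss arises because fewer subjects are at risk of new pain, which no questionnaire changes.

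**5. Effect on sizing a later trial.** Take the two ends of the 30–73% chronic-pain range in section 7 as new pain in controls, and assume that treatment halves it. For 80% power, n per arm = [1.96√(2m(1 − m)) + 0.842√(a(1 − a) + b(1 − b))]² / (a − b)², where a and b are the two proportions and m is their mean.

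| Control new pain | q = 0 | Any pain, q = 10% / 30% | New only, q = 10% / 30% |
|---|---|---|---|
| 30% | 121 | 181 / 353 | 138 / 188 |
| 73% | 28 | 34 / 51 | 36 / 56 |

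At the low end, counting new pain saves many subjects. At the high end it costs a few. The main reason to separate old from new pain is therefore interpretation.

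**The case against.** Several points against the concern stand.

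- A reader might infer that the comparison between arms is biased. It is not, in expectation: allocation is random and stratified by surgery type, so prior pain is balanced on average. What is lost is a clear meaning for the one-year result, some precision, and the means to see a chance imbalance at about 30 per arm.
- A reader might infer that all one-year incidence is contaminated. Phantom pain is recorded separately and cannot pre-exist as defined.
- A reader might infer that a baseline score would restore the whole fall in power from 41%. The fourth step above shows that it restores about 3 to 5 points under those inputs.
- A reader might infer that every cohort's main result would sharpen. Section 9 names range of motion for rotator cuff repair and knee arthroplasty, and FEV1 for VATS, as the end points of most interest. A pain score is not the baseline of those measures, and nothing in the documents makes it a strong covariate for them.
- The documents already say that a chronic-pain end point needs far more subjects than this study will enroll. The cohorts other than mastectomy are pilots without a predetermined primary endpoint. A few points of power would change no decision here.
- The table's title alone proves little, since a post-enrollment table need not list preoperative data. The omission rests on the available text as a whole.

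These points limit the size of the concern but do not remove it. Hypotheses 1b and 1c still predict a decrease in chronic pain at one year, and the data are still meant to inform the design of a later trial.

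**Conclusion.** The point holds as an inexpensive improvement to secondary and pilot outcomes. As written, the trial cannot separate pre-existing from post-surgical pain at one year for wound pain, the Brief Pain Inventory or the undefined chronic pain of Hypotheses 1b and 1c. It also cannot adjust pain severity for a baseline score. The arthroplasty, rotator cuff and amputation cohorts are the most exposed.

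The numerical gain ranges from negligible (under 2 points of power at r = 0.2) to material (about 19 points at r = 0.6, for a 0.6 SD effect). The documents supply neither the correlation, nor the share of subjects with persisting prior pain, nor the 0.6 SD effect, so these figures are illustrations. The dilution figures also assume that old pain persists equally in both arms.

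The documents do not support reading this as a flaw in the mastectomy day-2 primary result. At the plan's own 0.89 SD, a correlation of 0.2 or 0.3 adds only one or two points of power.

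**What to change.** Three changes:

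- Give the Brief Pain Inventory, with average and worst pain at the operative site, once after consent on the morning of surgery and before block and sedation. Add a preoperative column to the section 9 schedule.
- Adjust the pain-severity and Brief Pain Inventory analyses for that score. Tabulate it by arm within each surgery type.
- Define chronic pain for Hypotheses 1b and 1c. Report it at one year as new or increased relative to baseline, alongside any pain, and fix in advance what counts as increased.

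The cost is one short questionnaire, already used in the study, at a visit already held, plus changes to the schedule and analysis wording. Subjects without prior pain, probably including most mastectomy patients, gain little from it. No change to the sample size or to the day-2 primary test is needed.
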